**11.0 Statistics**

**12.0 Publication**

**13.0 References**

**14.0 Appendix**

14.1 Prothym – transthoracic echocardiogram (TTE) protocol

14.2 Performance status

14.3 CTC version 4.0

14.4 Masaoka-Koga staging system

14.5 WHO classification system of thymoma

## 1.0 Synopsis

Title of study	PROTHYM Trial  Proton radiotherapy of thymic malignancies  The study is supported by SLUSG, Swedish Lung Cancer Study Group
Principal investigator	[name] MD PhD
Co-investigators	[name] MD [name] Med Phys. PhD [name] MD [name] MD [name] [name] [name] [name] [name] MD [name] [name] [name] MD [name] [name] [name] MD [name], PhD
Study centres	Skandion Clinic, Uppsala, Sahlgrenska University Hospital, Gothenburg, Karolinska University Hospital, Stockholm, Akademiska Hospital, Uppsala, Norrlands University Hospital, Umeå, Örebro University Hospital, Linköping University Hospital, Skåne University Hospital, Lund
Study phase	Prospective, non-randomized phase II study
Number of patients	40 patients
Study Start	Sep 2017
Planned study period	Recruitment Start Date : Sep/2017 Target recruitment period:60 months Sep/2022) Follow up period. End date: 5 years from last treatment.
Study objectives	Primary : Toxicity (e.g. cardiac and pulmonary toxicity) and Local control at 5 year Secondary : PFS

	
Overall survival
 
Quality of life, measured by EORTC QLQ 30 + LC 14
 
Relapse pattern

Study design and plan	
This is a multicentre non-randomized phase II study of proton beam radiotherapy in patients with thymic epithelial tumours (i.e. thymoma and thymic carcinoma) in the post-operative setting or in inoperable patients with localized disease.
 
Patients not willing or for any reason unsuitable to undergo proton treatment will be asked to participate in a follow-up assessment after the regular photon treatment in the same manner as the included patients.

Methodology	
All doses are recorded in Gy(RBE).
 
After having checked all eligibility criteria patients will receive:
 
 
Patients with radical surgery and unfavourable histology (B2, B3, C) and/or Masaoka-Koga stage III, IVa: 2 Gy(RBE), once daily, five days a week to a total dose of 50 Gy(RBE).
 
Patients with non-radical surgery (R1 resection) regardless of stage and histology: 2.3 Gy(RBE), once daily, 5 days a week to a total dose of 57.5 Gy(RBE)
 
Inoperable patients regardless of stage and histology and patients with R2 non-radical resection: 2.5 Gy (RBE), once daily, 5 days a week to a total dose of 62.5 Gy(RBE)
 
Patients not willing to participate in study will receive photon therapy according to local practice (<math>\geq 45</math> Gy)
 
 
Induction or adjuvant chemotherapy may be used according to local practice. Concomitant chemotherapy is not allowed. For radiotherapy volumes see below.

Criteria for inclusion and exclusion	
Inclusion Criteria:

	
 
• Histological or cytological diagnosis of thymoma or thymic carcinoma.
 
• With radical surgery: stage III and IVa and selected stage II with type B2, B3 and thymic carcinoma according to local routine. With non-radical surgery (R1 or R2) or inoperable patient/ patient refusing surgery: stage I - IVa, any histology
 
• PS WHO 0 - 2.
 
• <math>\text{FEV}_1 \geq 1\text{L}</math> or <math>\geq 40\%</math> of predicted and CO diffusion capacity <math>\geq 40\%</math> of predicted (postoperative measures)
 
• Age <math>\geq 18</math> years, no upper age limit.
 
• Written informed consent from patients.
 
 
Exclusion Criteria:
 
 
• Masaoka-Koga stage IVb (distant metastases).
 
• Pregnancy.
 
• Serious concomitant systemic disorder incompatible with the study.
 
• Tumour motion <math>> 0.5</math> cm on two repeated 4DCT
 

Radiotherapy planning	
Treatment will be given by PBS (pencil beam scanning) technique at Skandion in Uppsala but all patients must have a photon backup plan, preferably with VMAT or IMRT technique.
 
 
• Pre-treatment preparation: Fixation, wingstep
 
• Pre-treatment imaging: 4DCT
 
• Specification of treatment prescription 
 
○ Volume specification: GTV, ITV, CTV, PTV, OAR's GTV = visible tumour growth CTV = post-operative tumour bed and/or defined margin to GTV: 0,5 cm to lung tissue and 1 cm elsewhere. Adjustment to airways, big vessels, bone will be performed. No adjuvant volumes, except for
 
 
 

	
pleura/ pericardium in between separate GTV's (stage IVa)
 
ITV includes CTV in all breathing phases defined according to local routines
 
<math>PTV = ITV + 5 \text{ mm}</math>. PTV is used for dose prescription and reporting according to ICRU recommendations
 
OAR's: heart, LADCA ,lung, spinal cord, esophagus
 
 
• Registration of volumes for GTV, PTV and doses to OAR's:           
 
Lung: <math>V_5</math>, <math>V_{20}</math>, <math>V_{40}</math>, MLD.
 
Esophagus: <math>D_{2\%}</math>, mean dose,
 
Heart: <math>D_{2\%}</math>, mean dose, <math>V_{40}</math>.
 
LADCA <math>D_{2\%}</math> and mean dose.
 
Spinal cord: <math>D_{2\%}</math> 
 
○ Absorbed dose prescription               
 
Group I: 2 Gy(RBE), once daily, five days a week to a total dose of 50 Gy(RBE), 5 weeks.
 
Group 2: 2.3 Gy(RBE), once daily, 5 days a week to a total dose of 57.5 Gy(RBE), 5 weeks.
 
Group 3: 2.5 Gy(RBE), once daily, 5 days a week to a total dose of 62.5 Gy(RBE), 5 weeks.
 
 
 
 
 
In case of interruptions for technical or administrative reasons the total treatment time should not exceed 6 weeks. If protons could not be delivered in stipulated 6 weeks photon back-up plan should be used instead.
 
 
 
• Relation to other therapies           
Up to three cycles of adjuvant/induction chemotherapy may be administered according to local routine. Radiation should start within 4-8 weeks after chemotherapy or surgery.
 
 

--	-------------------------------------------------------------------------------------------------------------------------------------------------------------------------------------------------------------------------------------------------------------------------------------------------------------------------------------------------------------------------------------------------------------------------------------------------------------------------------------------------------------------------------------------------------------------------------------------------------------------------------------------------------------------------------------------------------------------------------------------------------------------------------------------------------------------------------------------------------------------------------------------------------------------------------------------------------------------------------------------------------------------------------------------------------------------------------------------------------------------------------------------------------------------------------------------------------------------------------------------------------------------------------------------------------------------------------------------------------------------------------------------------------------------------------------------------------------------------------------------------------------------------------------------------------------------------------------------------------------------------------------------------------------------------------------------------------------------------------------------------

	
Pre-study evaluation:
 
The treatment should start within four weeks from registration.
 
The following are required prior to protocol entry:
 

• CT scan thorax not older than 4 weeks,

• Medical history

• Weight and length

• Physical examination

• Performance status according to WHO

• Assessment of quality of life according to QLQ 30+LC 14

• ECG

• Cardiac ultrasound

• Cardiac markers: NT-ProBNP and TNT

• Spirometry including CO diffusion capacity

• Assessment of symptoms at baseline according to NCI-CTCAE criteria version 4.0.

• Pregnancy test, if applicable

• Haematology      Haemoglobin

WBCC (White Blood Cells Count)

Platelets count

• Chemistry      CRP, serum creatinine

Serum calcium and albumin

Bilirubin, Alkaline Phosphates

LDH, ASAT and ALAT

	
Hematology and blood chemistry need to be reassessed if older than one week before treatment start.
 
UCG and ECG has to be performed within two weeks before start of treatment

	
On treatment evaluation:
 
 
• Recording of toxicity, performance status, ECG, NT-ProBNP, TNT, CRP at week 3 and end of treatment.
 
• Weight weekly. If weight change >5%, a new CT-scan and replanning should be considered.
 
• QLQ30 + LC14 at end of treatment
 
• At end of treatment visit patient shall be referred to TTE/UCG which shall preferably be performed one week after completion of therapy, but at least within two weeks
 
 
Follow up assessment:
 
First follow-up 4 weeks after completion of therapy and three months thereafter. Then every three months during the first two years. Thereafter every six months until end of study
 
 
• Recording of persistent or new toxicity
 
• Performance status
 
• Weight
 
• Tumour response evaluation with CT scan at 4, 7, 13 months and every 6 months thereafter or if clinically indicated.
 
• Spirometry including CO diffusion capacity at 6 months
 
• ECG at each visit the first year. Thereafter annually or if clinically indicated
 
• Cardiac markers: NT-ProBNP, TNT
 
• Quality of life according to QLQ30+LC14 at baseline, week 3 during treatment, 1, 3, 6 and 12 months after completed radiotherapy. Thereafter at 2, 3 and 5 years after treatment.
 

Statistical methods:	We will perform a Kaplan-Meier analysis with the aim to compare our data with published historic data from the ITMIG international database and other datasets. Toxicity data will be analysed descriptively and there will be a comparison between the proton patients and photon control group. 40 patients will be included in the study

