### **5.3 Treatment Schedule**

The study population will consist of three patient categories;

**A** patients who have undergone radical surgery

**B** patients who have undergone non-radical surgery

**C** patients who are considered inoperable.

Radiotherapy doses will differ between the groups. We have assumed that RBE for protons is 1.1 and the prescribed dose is the corresponding dose for photons (Gy(RBE)). Within brackets is the physical dose.

Patients who have undergone radical surgery but has an unfavorable histology (B2, B3, C) and/or Masaoka stage III or IVa (selected stage II-patients can be considered according to local practice) will receive 2 Gy(RBE) once daily, five days a week to a total dose of 50 Gy(RBE) (1.82 Gy OD, total dose 45.5 Gy)

Patients who have undergone non radical surgery (R1), regardless of stage and histology, will receive 2.3 Gy(RBE) once daily, five days a week, to a total dose of 57.5 Gy(RBE) (2.09 Gy OD, total dose 52.25 Gy)

Patients who are considered medically inoperable, or refuses surgery, regardless of stage and histology, and patients who have undergone R2 non-radical resection will receive 2.5 Gy(RBE) once daily, five days a week, to a total dose of 62.5 Gy(RBE) (2.27 Gy OD, total dose 56.75 Gy)

Patients not willing to participate in study, but willing to be included in follow-up according to study protocol will receive photon therapy according to local practice. The total dose must be  $\geq 45$  Gy.

Up to three cycles of chemotherapy may be administered prior to start of radiation according to local practice. Radiation therapy shall then start within 4-6 weeks after completion of the third cycle. Use of concomitant chemotherapy is not allowed.

If surgery has been performed, radiation therapy shall start 4-8 weeks thereafter

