## **6.2 Inclusion Criteria**

- Histological or cytological diagnosis of thymoma or thymic carcinoma
- With radical surgery stage III, IVa and selected stage II with type B2, B3 or thymic carcinoma according to local routine
- With non-radical surgery (R1 or R2), stage I - IVa, any histology
- Medically inoperable, or patient refusing surgery, stage I - IVa, any histology
- PS WHO 0 - 2.
- $FEV_1 \geq 1L$  or  $\geq 40\%$  of predicted and CO diffusion capacity  $> 40\%$  of predicted (post-operative measures).
- Age  $\geq 18$  years, no upper age limit.
- Written informed consent from patients.

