## **6.3 Exclusion Criteria**

- Masaoka-Koga stage IVb (distant metastases)
- Pregnancy.
- Serious concomitant systemic disorder incompatible with the study.
- Tumour motion  $> 0.5$  cm on two repeated 4DCT

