## 8.0 Radiotherapy

All patients included in the study must be able to receive prescribed dose to the target volume without exceeding absorbed doses to the organs at risk. Dose planning shall be performed with a CT-based system. A 4DCT for the planning is mandatory and has to be repeated before start of treatment. If tumour motion exceeds 0.5 cm proton therapy will not be given. All patients needs to have a photon backup plan, preferably with IMRT/VMAT technique although 3DCRT is allowed. Treatment planning can be performed on either average CT from the 4D-CT or a regular CT. Slice thickness is to be maximally 3 mm. If the photon plan is superior to the proton plan, the photon plan is to be used and the patient will be excluded from the study and followed up according to the photon cohort protocol.

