## **8.6 Patient monitoring before and during treatment**

Before treatment starts patients will undergo a control 4D-CT at Skandion Clinic. If tumour motion exceeds 0.5 cm proton treatment will not be given and patient will receive the photon backup plan instead.

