## **11.0 Statistics**

We will perform a Kaplan-Meier analysis with the aim to compare our data with published historic data from the ITMIG international database and other datasets. Since there is a limited amount of published thymoma data concerning heart we will also try to relate heart toxicity with published data from Hodgkin and breast cancer studies. Toxicity data will be analysed descriptively and there will be a comparison between the proton patients and photon control group. 40 patients will be included in the study

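### The photon comparison group is defined inconsistently, and the synopsis wording lets in patients who failed the fitness criteria that proton patients must meet

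*Protocol*

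**What the plan says.** The protocol describes entry to the photon group in several places.

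- **Synopsis, study design and plan:** "Patients not willing or for any reason unsuitable to undergo proton treatment will be asked to participate in a follow-up assessment" after regular photon treatment, in the same manner as included patients.
- **Synopsis, methodology:** the photon line names only patients unwilling to take part. It stands in a treatment list introduced by a statement that eligibility has been checked.
- **Section 5.3:** "Patients not willing to participate in study, but willing to be included in follow-up according to study protocol will receive photon therapy". The one treatment condition is a dose floor: these patients "will receive photon therapy according to local practice. The total dose must be" at least 45 Gy.
- **Section 8.0:** if the photon plan is superior, "the patient will be excluded from the study and followed up according to the photon cohort protocol".
- **Section 8.6:** "If tumour motion exceeds 0.5 cm proton treatment will not be given and patient will receive the photon backup plan instead".

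Sections 6.2 and 6.3 set the criteria for the study population. They include WHO performance status 0 to 2, floors for FEV1 and CO diffusion capacity, and exclusion for stage IVb, pregnancy, tumour motion above 0.5 cm, or a "Serious concomitant systemic disorder incompatible with the study". Neither section mentions the photon group.

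Section 4.1.1 makes toxicity, with cardiac and pulmonary toxicity as examples, a primary objective. Section 11.0 and the synopsis state that toxicity will be analysed descriptively and that "there will be a comparison between the proton patients and photon control group".

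**The concern.** A non-randomised comparison is only as good as the definition of its comparator. Here the proton group must pass a fitness screen, while the comparator may include people who did not. Poor lung function, poor performance status and serious comorbidity are grounds for failing section 6. They are also plausible causes of recorded cardiac and pulmonary events, whatever radiation is given. If such patients enter the photon group, protons gain an apparent safety advantage that owes nothing to the treatment.

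The inconsistency also has a practical effect. A site that follows section 5.3 would offer follow-up only to decliners, while a site that follows the synopsis would offer it to a wider group. The comparator would then depend on which page a site had read.

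**Working it through.** **1. Routes into the photon group, side by side**

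| Place | Who | Section 6 stated to apply? |
|---|---|---|
| Synopsis, study design | Unwilling, or unsuitable for protons on any ground | No |
| Synopsis, methodology | Unwilling only | Arguably, through the lead-in to the list |
| Section 5.3 | Unwilling, but agree to follow-up | No |
| Section 8.0 | Photon plan superior; excluded from the study | No; refers to a photon cohort protocol that is not shown |
| Section 8.6 | Tumour motion above 0.5 cm; treated with the photon backup plan | No; motion is itself a section 6.3 exclusion |

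The first row is wider than the second and third. The fourth adds a group that the second and third do not name. The fifth gives the treatment but does not say whether these patients join the photon cohort, although the first row would invite them.

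**2. Does section 6 reach the photon group by implication?** Not clearly. The synopsis has photon patients followed like the included patients, which treats them as a separate set. Section 8.0 calls one route an exclusion from the study. Section 6.3 cannot apply in full if patients with excessive motion are to be followed. The eligibility lead-in in the synopsis methodology precedes a photon line that covers decliners only, so it does not reach the unsuitable patients of the design paragraph.

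**3. What size could the effect have?** The plan has no figure to reproduce: it gives 40 patients, no photon group size and no toxicity rates. The following is an illustration in which every rate and share is assumed and there is no true difference between modalities.

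Let *p* be the toxicity rate in patients who meet the fitness criteria, *q* the rate in those who do not, and *s* the share of the photon group who do not.

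- Photon rate = (1 − *s*)·*p* + *s*·*q*
- Spurious difference = *s*·(*q* − *p*)

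With *p* = 10%:

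| *q* | *s* = 0 | *s* = 25% | *s* = 50% | *s* = 75% |
|---|---|---|---|---|
| 20% | 0 | 2.5 points | 5 points | 7.5 points |
| 30% | 0 | 5 points | 10 points | 15 points |
| 40% | 0 | 7.5 points | 15 points | 22.5 points |

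For example, *q* = 30% and *s* = 50% give a photon rate of 0.5 × 10% + 0.5 × 30% = 20%, against 10% for protons.

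**4. Would the data reveal it?** Probably not. With a 10% rate in both groups, the 95% half-width of the difference is 1.96 × √(0.09/40 + 0.09/*n*), where 0.09 = 0.10 × 0.90 and *n* is an assumed photon group size. This is about 16 points for *n* = 20 and about 13 points for *n* = 40. Most of the differences in the table lie within that noise, so the outcome data alone could not show that selection was at work.

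**The case against.** The strongest reply is that being unsuitable for proton treatment is not the same as being ineligible for the study. Performance status, lung function and comorbidity are not specific to protons. Every route from protons to photons that the protocol spells out is technical, anatomical or logistic: tumour motion, a superior photon plan, or protons not deliverable on schedule (sections 5.4 and 8.7). No section sends a patient who failed a fitness criterion to the photon cohort. The eligibility lead-in in the synopsis and the photon cohort protocol cited in section 8.0 may also mean that criteria were intended.

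This stands against a stronger reading. A reader might infer that the photon group will be filled with unfit patients and that protons will therefore look safer. The documents do not support that: decliners may be fully eligible, and entry of unfit patients is permitted by the synopsis wording but nowhere described. The net direction is not shown either. Photon patients may receive as little as 45 Gy, while proton patients are prescribed 50 to 62.5 Gy(RBE), and this difference could push toxicity the other way.

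The reply does not remove the inconsistency. The synopsis sets no limit on the grounds for unsuitability, and no text shown closes that opening.

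Two further replies are that the comparison is descriptive and that restriction or adjustment belongs in the analysis plan. A descriptive difference is distorted by selection as much as a tested one. Adjustment can be left to an analysis plan, but who enters the comparison group, and conflicting protocol text about it, is a protocol matter.

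**Conclusion.** The point holds as a defect in the definition of the comparator. The descriptions of the photon group do not agree, section 6 is not stated to apply to it, and the widest description permits patients who failed the fitness criteria to enter the group against which a primary objective is compared. This can bias the toxicity comparison in favour of protons.

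The size is unknown. It is zero from this source if all photon patients meet sections 6.2 and 6.3 apart from tumour motion. Under the assumed rates and shares above it runs from 2.5 to 22.5 percentage points, but that range shows only how the bias scales and is no estimate for this trial. The overall direction of bias, with dose and other differences included, cannot be settled from the protocol.

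**What to change.** - Give one definition of the photon cohort, in section 6, and bring both synopsis entries and sections 5.3, 8.0 and 8.6 into line with it. If the photon cohort protocol named in section 8.0 already holds criteria, state or reference them there.
- State that every criterion in sections 6.2 and 6.3 that is not specific to protons, that is, all except tumour motion, defines the photon comparison cohort.
- Record the reason for photons in the CRF: declined, tumour motion, superior photon plan, or other unsuitability.
- Limit the toxicity comparison in section 11.0 to photon patients who meet those criteria. Others may still be followed, but are reported separately.

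The cost is protocol wording, one CRF field and a somewhat smaller comparison group. No patient's treatment changes.

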## 2.0 Abbreviations

AE	Adverse event
ALAT	Alanine aminotransferase
ASAT	Aspartate aminotransferase
CO-diff	Carbon oxide diffusion
CRP	C-reactive protein
CT	Computed tomography
4DCT	4-dimensional computed tomography
CTCAE	Common terminology criteria for adverse events
CTV	Clinical target volume
ECG	Electrocardiography
EORTC	Europena Organization for Research and Treatment of Cancer
FEV1	Forced expiratory volume, one second
Gy	Gray
Gy(RBE)	RBE-weighted absorbed dose in Gy
GCP	Good Clinical Practice
GTV	Gross tumour volume
βHCG	Human Chorionic Gonadotropin
ICRU	International Commission on Radiation Units and Measurements
IMRT	Intensity-modulated radiotherapy
ITMIG	International Thymic Malignancy Interest Group
LADCA	Left anterior descending coronary artery
LC14	Lung Cancer 14, QL-questionnaire
LDH	Lactate dehydrogenase
NCI	National Cancer Institute
NT-ProBNP	N-terminal pro b-type Natriuretic Peptide
OAR	Organ at risk
OD	Once daily
OS	Overall survival
PBS	Pencil beam scanning
PFS	Progression-free survival

PORT	Post operative radiotherapy
PS	Performance status
PTV	Planning target volume
RBE	Relative Biological Effectiveness
R1	Microscopic residual tumour directly at the resection margin
R2	Macroscopic residual tumour locally
RIHD	Radiation induced heart disease
RILD	Radiation induced lung disease
SAE	Serious adverse event
TET	Thymic epithelial tumour
TnT	Troponin T
UCG	Ultrasonic cardiography
VMAT	Volumetric modulated arc therapy
QLQ30	Quality of life questionnaire

